Experimental arm participants will receive the RAPIDS intervention, which includes education about the dangers of IMF, motivational interviewing to increase willingness to use fentanyl test strips and engage in overdose risk reduction behaviors, hands-on training to use the test strips, and opportunities to plan and role- play how to implement overdose risk reduction behaviors upon receipt of a positive or negative test result. In addition, intervention participants will receive ten test strips for personal use. Motivational interviewing “booster” sessions will occur at 1, 2, and 3 months post-randomization, with additional test strips provided on an as needed basis. In the attention-matched control arm, participants will receive standardized overdose education and naloxone distribution (OEND) training, with attention-control visits at 1, 2, and 3 months.

Participants in both arms will receive a naloxone kit after completion of the first session, and information regarding where to obtain additional naloxone at subsequent visits. Follow-up interviews will occur at 6 and 12 months. The primary endpoint will be the rate of self- reported overdose over the follow-up period. Secondary endpoints (e.g., accidental overdose death and suspected EMS runs for overdose) will be ascertained by data linkage to statewide overdose surveillance databases maintained by the research team. Consistent with recruitment rates in our prior studies, we aim to enroll 20 participants per month starting in Year 1 until target

enrollment is reached.

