### **3.1 b. Detailed description of the RAPIDS intervention (Experimental Arm)**

The intervention is based on two behavioral frameworks: the **Information-Motivation-Behavior (IMB) model**, and the **self-efficacy model** as applied to addictive behaviors.

**The RAPIDS intervention provides** (see also **Figure 4** from grant proposal):

[figure not shown]
1. education about the dangers of IMF and how to prevent overdose (information);
2. motivational interviewing to encourage risk reduction behaviors (motivation) and to assess and improve participants' confidence in implementing these behaviors (self

efficacy);

3. hands-on training demonstrating how to use and interpret fentanyl test strips (behavioral skills), including opportunities to practice using the test strips; and
4. provision of BTNX Rapid Fentanyl test strips (see **Attachment B**) for personal harm reduction use.

Specifically, the intervention will directly increase engagement in the target overdose risk reduction behaviors, and indirectly through fentanyl test strip utilization. In other words, **we hypothesize that fentanyl test strip utilization is an important, but not exclusive, behavioral mediator through which the intervention will prevent overdose among PWUD.**

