**Reports of Prior Investigations:** To examine the feasibility and acceptability of using test strips to identify fentanyl contamination of illicit drugs prior to consumption, we conducted a pilot study involving 93 participants. After a brief training and being offered 10 test strip to use at home, willingness to use the test strips was high; overall, 95% agreed or strongly agreed that they planned to use the tests. Almost all pilot study participants (99%) reported that it would be easy to use the test strips to identify fentanyl contamination in illicit drugs prior to consumption. Among persons who returned for follow-up, a total of 62 participants (77%) reported using at least one test strip. Of these, 31 (50%) received at least one positive result. A positive result was associated with older age, homelessness, heroin use, injection drug use, ever witnessing an overdose, and concern about overdose or drugs being laced with fentanyl (all  $p < 0.05$ ). Receiving a positive result was significantly associated with reporting a positive change in overdose risk behavior between baseline and follow-up ( $p \leq 0.01$ ). Among all participants, 79 (98%) reported confidence in their ability to use the test strips and 77 (95%) wanted to use them in the future. A subsequent qualitative study found that the vast majority of participants found

 Johns Hopkins University. The FORECAST Study. Available from: [https://americanhealth.jhu.edu/sites/default/files/inline-files/Fentanyl\\_Executive\\_Summary\\_032018.pdf](https://americanhealth.jhu.edu/sites/default/files/inline-files/Fentanyl_Executive_Summary_032018.pdf)

 Krieger MS et al. High willingness to use rapid fentanyl test strips among young adults who use drugs. *Harm Reduction Journal*. 2018;15:7.

 Krieger MS et al. Use of fentanyl test strips among young adults who use drugs. *International Journal of Drug Policy*. 2018;61:502-508.

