In two per-protocol sub-analyses, we will determine the effect of the intervention on the primary study endpoint among those who: (1) reported using fentanyl test strips during at least one intervention visit (months one, two, and three) compared to all participants assigned to the control arm; and (2) participants who completed one, two, and all three intervention visits using an ordinal variable, compared to all participants assigned to the control arm.

Finally, to account for potential treatment contamination (e.g., use of fentanyl test strips in the control arm, lack of use in the treatment arm), we will employ an instrumental variable approach to estimate the contamination-adjusted intention to treat (CA ITT) effect. We will consider 'receipt of treatment' to be self-reported use of fentanyl test strips at months one, two, or three follow-up visits.

Examine whether the treatment effect is mediated by differential uptake of risk reduction behaviors in the intervention arm (Aim 2). If the RAPIDS intervention shows efficacy in reducing overdose rates among the sample (Aim 1), we will explore the extent to which this relationship works through several possible mediators. For mediation analyses, first, we will examine, in multivariable regression models, which mediators, if any, are significantly changed by the intervention (i.e., the rate of change differed by treatment assignment). For those that are significantly impacted by the intervention, we will conduct path analysis using structural equation modeling to determine whether the effect of the intervention on overdose was through the hypothesized mediator(s). Structural equation modeling (SEM) allows for the simultaneous estimation of total, direct, mediated and indirect effects of a causal variable (i.e., the intervention) on the outcome (i.e., overdose) through a set of mediator variables. SEM can handle outcomes and mediators with a variety of distributions (including, Gaussian, Poisson and Binomial). Inferences for indirect effects can be estimated using bootstrapped confidence intervals.

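### The contamination-adjusted ITT analysis counts test-strip use as the only treatment received, but the protocol also hypothesises a non-strip route, so the estimate does not identify the effect of strip use

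*SAP*

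**What the plan says.** The Aim 1 part of SAP section 3 closes with a supplementary analysis: "we will employ an instrumental variable approach to estimate the contamination-adjusted intention to treat (CA ITT) effect". The contamination in view is "use of fentanyl test strips in the control arm, lack of use in the treatment arm". The exposure is then fixed: "We will consider 'receipt of treatment' to be self-reported use of fentanyl test strips at months one, two, or three follow-up visits". The SAP names neither the instrument nor the effect scale. Randomised arm is the evident instrument, because the aim is to adjust an ITT contrast.

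Protocol 3.1b sets out the causal model. It says that "the intervention will directly increase engagement in the target overdose risk reduction behaviors, and indirectly through fentanyl test strip utilization", and hypothesises that "fentanyl test strip utilization is an important, but not exclusive, behavioral mediator through which the intervention will prevent overdose among PWUD". Two of its three target behaviours, not using alone and having naloxone within reach, need no strip.

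Protocol 3.1a gives the experimental arm education on illicit fentanyl and "motivational interviewing to increase willingness to use fentanyl test strips and engage in overdose risk reduction behaviors", with boosters at months 1, 2 and 3. Control receives standard overdose education with naloxone, and attention visits on the same schedule. The survey in Attachment A agrees. Section G (experimental arm) has staff record behaviour-change goals, readiness and confidence. Section H (control) has a naloxone video and demonstration at baseline plus questions for people who have used strips, and no goal-setting.

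Neither document states the exclusion restriction, argues for it, or plans a sensitivity analysis for its failure.

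**The concern.** An instrumental-variable estimate divides the arm effect on the outcome by the arm effect on the exposure. The result is the effect of the exposure (in those whose use depends on assignment) only if arm reaches the outcome solely through that exposure. Here the exposure is strip use alone, while the trial's own model has a second path. Any benefit or harm from the other components is put into the numerator and credited to strips.

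What is at stake is attribution and size. The test of no arm effect is essentially the ITT test, so this analysis does not create a spurious overall effect. But a programme could hand out strips without motivational interviewing, and SAP section 5 says the data may serve public health planning. A figure that mixes the two would mislead such a programme, and nothing in the result would show that it had.

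**Working it through.** **The plan's own figure.** SAP section 6 assumes 20% overdose in control, a 50% reduction, 250 per arm and 80% retention, with power above 80%. For 20% v 10%, 200 evaluable per arm and two-sided alpha 0.05:

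- SE under the null = √(2 × 0.15 × 0.85 / 200) = 0.0357
- SE under the alternative = √((0.16 + 0.09) / 200) = 0.0354
- power = Φ((0.10 − 1.96 × 0.0357) / 0.0354) = 80.2%

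The stated power reproduces, so a 10-point ITT reduction is the planning effect. The documents give no figure for the instrumental-variable analysis itself.

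**Inputs.**

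- ITT reduction: 10 points (SAP section 6).
- Strip use in the intervention arm: Attachment H reports from the pilot that "a total of 62 participants (77%) reported using at least one test strip". The denominator there is people who returned for follow-up. Counting all 93 enrolled, 62/93 = 67%.
- Strip use in control: not given. Assumed 20%, range 0% to 40%.
- Direct share of the arm effect: not given. Varied from 0 to 100%, plus an opposite-direction case.

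**Formulas.** Estimate = ITT / (use in intervention − use in control). True strip effect = (ITT − direct effect) / the same difference.

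**Results (reduction in points, 20% use in control).** The estimate is 10/0.57 = 17.5 at 77% use and 10/0.467 = 21.4 at 67% use, whatever the direct share. The true strip effect is:

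| Direct effect (points) | 77% use | 67% use |
|---|---|---|
| 0 | 17.5 | 21.4 |
| 2.5 (25%) | 13.2 | 16.1 |
| 5.0 (50%) | 8.8 | 10.7 |
| 7.5 (75%) | 4.4 | 5.4 |
| 10 (100%) | 0 | 0 |
| −2.5 (opposite direction) | 12.5/0.57 = 21.9 | 12.5/0.467 = 26.8 |

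**Range over control use (77% in intervention).** At 0%, 5%, 20%, 30% and 40% the estimate is 13.0, 13.9, 17.5, 21.3 and 27.0 points. With half the effect direct, the true strip effect is half of each: 6.5, 6.9, 8.8, 10.6 and 13.5.

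**Simulation check.** With 2 million participants per scenario, additive risks, monotone uptake and 20% control use, the estimates were 17.7, 17.6 and 17.5 points for direct shares of 0, 50 and 100%. The true strip effects were 17.5, 8.8 and 0. The estimate does not move as the strip effect vanishes.

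**The case against.** Several points on the other side stand.

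- **The direct route is a hypothesis.** A reader might infer that the exclusion restriction must fail. The documents support less: it contradicts the trial's stated causal model, and would still hold if the non-strip components turned out to have no effect on overdose.
- **The direct path is narrowed.** Naloxone, basic overdose education and the visit schedule are matched, and both arms get a wallet card with fentanyl information. Role-play should not be counted as a direct component: protocol 3.1a ties it to responding to a test result, and 3.1b does not name it. In-person fentanyl education and motivational interviewing remain.
- **The sign is not settled.** A reader might infer that the estimate always overstates the strip effect. The primary endpoint is non-fatal overdose. Using in company with naloxone at hand mainly changes what follows an overdose, and could raise recorded non-fatal events through survival or emergency calls. Practices such as a lower initial dose could prevent overdose. Either direction is possible.
- **The SAP does not call the result a strip effect.** That is true, but the exposure definition makes it a per-user figure, which invites that reading.
- **Other analyses are adjacent.** The second per-protocol analysis uses visits completed. Aim 2 separates direct from mediated effects, but it runs only if efficacy is shown, takes only mediators that the intervention significantly changed, and leaves this estimate uncorrected.

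**Conclusion.** The point holds as a limit on what this supplementary analysis can show. With receipt defined as strip use alone and arm as the instrument, the estimate does not identify the effect of strip use under the protocol's own model. On the planning effect it would read 17.5 points (21.4 at 67% use) where the strip effect is 8.8 (10.7) if half the arm effect is direct. It would understate the strip effect if the direct effects were harmful.

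These figures rest on an assumed control-arm uptake, assumed direct shares, pilot uptake as a proxy for the trial, and a risk-difference scale. The primary model is time-to-event, and the SAP sets no scale for this analysis, so they illustrate size and do not predict the result.

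A reader might also take the estimate as an upper bound on the strip effect. That needs direct effects in the same direction and accurately reported strip use. Over-reporting in the intervention arm widens the apparent uptake gap and shrinks the estimate. Nothing here bears on the primary ITT comparison.

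**What to change.** Name the instrument and the effect scale in the SAP, then take one of two routes.

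1. Define receipt of treatment as receipt of the intervention package, measured by sessions delivered. The exposure then includes the non-strip components.
2. Keep strip use as the exposure, and:
   - state that the exclusion restriction is not expected to hold under the model in protocol 3.1b;
   - do not present the estimate as the effect of strip use;
   - add a sensitivity table that removes 0, 25, 50 and 75% of the ITT effect as direct, plus an opposite-direction case, before scaling by the observed uptake difference;
   - use the term upper bound only with the two conditions on direction and accurate reporting stated beside it.

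The cost is SAP wording and one table. Data collection does not change.

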# **THE RAPIDS CLINICAL TRIAL:**

## **Appendix B: RAPIDS Protocol**

### **PROTOCOL NARRATIVE Aims & Methodology**

#### **3.1a. Specific Aims & Methodology**

In light of the urgent need for research on novel interventions to prevent illicitly-manufactured fentanyl (IMF) exposure and overdose, we will determine whether a brief, theory-driven overdose prevention intervention incorporating “take home” rapid fentanyl testing decreases overdose among adults. We will enroll up to 550 PWUD at risk of overdose in a randomized trial, hereby referred to as the **Rhode Island Prescription and Illicit Drug Study (RAPIDS)**.

In **Aim 1**, we will assess the efficacy of the RAPIDS intervention on preventing overdose among PWUD. In **Aim 2**, we will determine whether the intervention effects are mediated through our model constructs, including knowledge, motivation, behavioral skills, and self-efficacy to use the fentanyl test strips and engage in overdose risk reduction practices. In **Aim 3**, we will determine whether there is heterogeneity of treatment effect related to key participant characteristics, including age, baseline motivations to use the test strips, as well as type and frequency of drug use. By determining the sub-groups for whom intervention efficacy is highest, these findings will guide optimal implementation of this brief intervention to reduce overdose among PWUD.

Eligibility criteria include reported use of heroin, illicit stimulants, counterfeit prescription pills, or injection drug use in the past 30 days, regardless of treatment status (see **Table 1**). An overview of the study design is included in section **3.1.d** below. Participants will be randomized 1:1 to receive the RAPIDS intervention or the attention-matched control condition.

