#### Assessing intervention efficacy in reducing fatal and nonfatal overdose (Aim 1, primary endpoint).

The primary outcome will be **non-fatal overdose**, defined as a composite outcome, consisting of one of the following:

1. A self-reported overdose ascertained at the six and/or 12 month follow-up visits;
2. A non-fatal opioid overdose identified in the Rhode Island EMS database, using a case definition for suspected overdose developed by RIDOH previously;
3. An emergency department encounter for an accidental drug overdose that did not result in death, using a case definition developed by the CDC;

The primary analysis will be conducted using a survival framework, with time to *first* nonfatal overdose—identified through any of the data sources noted above—serving as the primary outcome. For self-reported data, event times will be estimated from SAE reports (in which participants are asked to estimate the date of their overdose). Participants will be right-censored as of the date of the first

---

 <https://www.ncbi.nlm.nih.gov/pmc/articles/PMC7948191/>

outcome event or at the end of the follow-up period, defined as 15 months following the participant's baseline visit.

To account for potential imbalance and to improve statistical efficiency, we will adjust for known or anticipated prognostic variables measured at baseline. These variables will include sociodemographic characteristics (e.g., age, gender identity, race/ethnicity), recent criminal justice involvement, housing instability, and substance use patterns including injection drug use & history of overdose. Variables will be transformed or categorized as necessary to address skewed or imbalanced data. We will also adjust for pre-baseline EMS runs for suspected opioid overdoses and ED encounters for drug overdoses using the case definitions noted above, occurring up to six months prior to the date of the participant's baseline visit.

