Determine whether intervention efficacy varies across participant subgroups (Aim 3). This is an exploratory aim. We will examine if heterogeneity of intervention effect is modified by key baseline characteristics of interest, including: age; sex; type, frequency, and route of drug use; baseline level of overdose risk (e.g., lifetime history of overdose); and pre-intervention motivations for fentanyl test strip utilization. We will perform stratified subgroup analyses to determine if treatment effects vary between groups of individuals.

---

 [10.1136/bmj.c2073](https://doi.org/10.1136/bmj.c2073)

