#### **6. Sample Size Calculations**

We provide power calculations for key outcomes below, based on an enrollment of 500 participants (n=250 per arm). To ensure we have a sufficient number of participants and to account for attrition,

we have received IRB approval to enroll up to 550 if necessary. The following assumptions are based on findings from our pilot intervention study. First, at baseline, 37% of participants reported a lifetime history of overdose, and 11% reported an overdose in the past six months. As such, for the primary analyses, we assumed that 20% of participants in the control arm will experience an overdose during the 12-month follow-up period. Second, we conservatively assumed an 80% retention rate in the trial, although we were able to retain 90% of pilot participants.

Given these assumptions, we have >80% power to detect a 50% reduction in overdoses. Similar effect sizes were assumed for an ED-based overdose prevention intervention, and have been deemed as a benchmark for success by key stakeholders. For the exploratory endpoint in Aim 1 (time to first fatal overdose or suspected overdose resulting in an EMS record), we conservatively assumed that only 38% of self-reported overdoses would result in death or attendance by EMS, based on previously published data, for a rate of 8 per 100 person-years in the control arm. We have  $\geq 80\%$  power to detect a 50% reduction in the hazard of fatal overdose or ED visit for an overdose.

Finally, we used a method to estimate sample size for evaluating mediation by joint testing of both links in an indirect pathway from exposure to mediator to outcome (Aim 2). Given the assumptions described above, we have >80% power to detect a statistically significant mediated effect for a coefficient for exposure on mediator and mediator on outcome of at least 0.8 (i.e., a relative risk of  $\exp[0.8] \cong 2.3$ ), respectively.

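### Exploratory Aim 3 asks whether the effect differs across seven baseline factors but plans only stratified analyses, with no interaction test or other comparison of strata

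*SAP*

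**What the plan says.** SAP section 3 (Data Analysis Plan), Aim 3, states "This is an exploratory aim". Its open-ended list of factors begins with age, sex, and the kind, frequency and route of drug taking, and continues with "baseline level of overdose risk (e.g., lifetime history of overdose); and pre-intervention motivations for fentanyl test strip utilization". Counting kind, frequency and route separately, that is seven factors. The only method is then given: "We will perform stratified subgroup analyses to determine if treatment effects vary between groups of individuals".

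Protocol section 3.1f and Protocol Attachment F, section C1, carry the same method sentence, without the exploratory label. Protocol section 3.1a states the intended use: "By determining the sub-groups for whom intervention efficacy is highest, these findings will guide optimal implementation".

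The only interaction term in either document is treatment by time, in the protocol's mixed model for Aim 1 (Attachment F, C1). The SAP's other stratified analysis, by number of completed outcome visits, is a missing-data check. For the main comparison, the SAP says: "The primary analysis will be conducted using a survival framework", adjusted for baseline prognostic variables.

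**The concern.** Whether an effect varies between groups is a question about the difference between two effects. An estimate and p-value inside each stratum do not answer it, and the plan gives no rule for setting one stratum against another. In practice, such tables are easily read by which strata reach significance. Each stratum has much less power than the whole trial, so under that reading an intervention that works equally well in everyone will often seem to work in one group and not in another.

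The protocol intends the subgroup findings to guide implementation. A false contrast could therefore steer test strips away from people who benefit. The exploratory label limits the strength of any claim, but it does not supply a valid comparison.

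**Working it through.** **Inputs from the documents.** SAP section 6: 250 per arm, 80% retention, hence 250 × 0.80 = 200 per arm; control risk from "we assumed that 20% of participants in the control arm will experience an overdose during the 12-month follow-up period"; a 50% reduction, hence 10% in the intervention arm; and "37% of participants reported a lifetime history of overdose". Protocol Attachment F, B1: 33% female. Two-sided 5% level (SAP section 4).

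**Assumptions of mine.** Each factor is split in two. Strata are read by p<0.05 within stratum. The true effect is the same in everyone.

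**1. The plan's own power.** With a pooled-variance test of two proportions, power = Φ{[δ√n − 1.96√(2p̄(1−p̄))] / √(p₁q₁+p₂q₂)}.

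At n = 200: [0.1×14.142 − 1.96×0.505] / 0.5 = 0.849, so power is 80.2%. This agrees with the SAP's claim of more than 80%.

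**2. One factor, uniform design effect.** In an equal half, n = 100 per arm: [0.1×10 − 1.96×0.505] / 0.5 = 0.02, so power p = 50.8%. The chance that exactly one half is significant is 2p(1−p) = 2×0.508×0.492 = 50%.

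| Setting (per factor) | Stratum powers | Exactly one significant |
|---|---|---|
| Equal halves, 20% vs 10%, 200/arm | 0.51, 0.51 | 50% |
| 37/63 (prior overdose), same rates | 0.40, 0.60 | 52% |
| 33/67 (female), same rates | 0.36, 0.63 | 54% |
| Equal halves, 20% vs 10%, 250/arm | 0.60, 0.60 | 48% |
| Equal halves, 20% vs 15%, 200/arm | 0.154, 0.154 | 26% |
| Equal halves, no effect | 0.05, 0.05 | 9.5% |

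**3. Seven factors.** All seven splits divide the same trial, so they share one overall result and cannot simply be multiplied as independent. Write the two half-sample statistics for a factor as (Z+D)/√2 and (Z−D)/√2. Z is the overall statistic, common to all factors, with mean equal to the trial's drift. D is a standard normal contrast for that factor. With q(z) the chance that exactly one half exceeds 1.96 in absolute value given Z = z, the chance of at least one contrast is 1 − E[(1 − q(Z))⁷] when the D are unrelated. The last column instead assumes correlation 0.5 between the D.

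| Uniform effect | Drift | Unrelated | Correlation 0.5 |
|---|---|---|---|
| 20% vs 10%, 200/arm | 2.81 | 87% | 84% |
| 20% vs 10%, 250/arm | 3.16 | 85% | 81% |
| 20% vs 15%, 200/arm | 1.32 | 60% | 54% |
| None | 0 | 34% | 29% |

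The expected number of false contrasts at the design effect is 7 × 0.50 = 3.5 of 7 (7 × 0.48 ≈ 3.3 with 250 per arm). A patient-level simulation with exponential event times (200 per arm, 6,000 trials) gave 0.51 per factor and 0.88 over seven.

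**4. The interaction test.** Its error is about 5% per factor whatever the uniform effect. Over seven independent unadjusted tests it is 1 − 0.95⁷ = 30%; with Bonferroni it is at most 5%. The same patient-level simulation gave 0.046 per factor and 0.28 over seven.

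**5. Power of the interaction test.** At the design rates each equal half has 100 × 0.20 = 20 control events and 100 × 0.10 = 10 intervention events. The standard error of the log ratio of hazard ratios is √(1/20+1/10+1/20+1/10) = 0.548. For 80% power the ratio must be about exp(2.8 × 0.548) = 4.6. If risk is halved in one half and unchanged in the other, power is about 32% (Wald test on the log odds-ratio scale).

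**The case against.** The SAP does not commit to reading strata in isolation. It states an intent to see whether effects vary, stratified estimates with intervals can be compared, and a stratified analysis often includes a homogeneity test. On this view the plan is silent on the comparison rather than wrong. That is a fair account of the wording, but the comparison is still missing, and it is the part that answers the aim's question.

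The contrast percentages measure a reading rule the SAP does not contain, applied to two-way splits it does not define. This stands: they illustrate what the gap permits and are not the error rate of a planned procedure. They also use 12-month planning proportions, whereas the primary analysis is time to first event from three sources with follow-up to 15 months. Event counts, and so stratum power and the 4.6, could differ.

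With no treatment effect, reading by stratum (34%) is barely worse than seven unadjusted interaction tests (30%). This also stands. The large difference arises when the intervention works uniformly, which is when subgroup findings are most likely to be used.

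Finally, the aim is exploratory, and the primary estimate, sample size and stopping rules are untouched. This limits the severity but does not remove the point.

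**Conclusion.** The concern holds. The plan asks whether the effect differs by seven factors, and neither document names a method that tests a difference. This conclusion rests on the text and does not depend on any calculation. The size does depend on assumptions: two strata per factor, reading by p<0.05 within stratum, the SAP's planning rates and a uniform effect. On those, a false contrast occurs about half the time per factor and in about 84% to 87% of trials over seven factors at the design effect with 200 per arm, falling to about 29% to 34% with no effect. The sponsor should correct it, but because the aim is exploratory the validity of the primary result is not at stake.

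**What to change.** In SAP section 3, Aim 3, and in the matching protocol text:

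- For each listed factor, add a treatment-by-factor interaction to the primary time-to-event model, with the factor's categories or continuous form fixed in advance.
- Judge heterogeneity on that term and its confidence interval.
- State that the results are exploratory, and whether they are adjusted for seven factors. Without adjustment about 30% of trials would show at least one false interaction; Bonferroni holds this to at most 5%.
- Report stratum hazard ratios with confidence intervals as description only.

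The cost is SAP wording and one extra model term per factor. The drawback is low power: only very large differences between strata (a ratio of hazard ratios near 4.6) would be detected reliably, so few subgroup claims will be possible. The implementation statement in Protocol section 3.1a should be tempered to match.
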